10.5.2.4 BDI-II

The BDI-II²¹ consists of 21 items; each item is a list of four statements arranged in increasing severity about a particular symptom of depression. Each statement is scored from 0 to 3. Each of the 21 items is summed to give a single score for the BDI-II.

10.5.2.5 PGIC

The PGIC is a single-item rating by subjects of their improvement with treatment during a clinical trial.²² It asks the subject to rate their improvement with therapy on a 7-point scale ranging from very much worse to very much improved, with no change as the mid-point.

11. Study Oversight

11.1 Within-subject stopping criteria

Administration of IMP will continue within an individual subject if, in the investigator's opinion, it is safe to do so.

The following criterion constitutes a contraindication to further administration of IMP to an individual subject:

 Any experience, which is considered, by the investigator and/or the sponsor to be serious, and severe and clinically significant, which would suggest significant hazard that may be associated with the use of the IMP

If the above criterion becomes applicable during the study, the subject must not receive further doses of IMP. Such subjects will be withdrawn and follow the withdrawal procedures as described in Section 5.7.

11.2 Suspension or premature termination of the study

Conditions may arise during the study that could prompt the study to be halted or the study site to be terminated. The sponsor may terminate part of, or the entire study for safety, administrative, or commercial reasons. Conditions that may prompt such considerations include, but are not limited to, the following:

- The discovery of unexpected, serious, or unacceptable risk to subjects enrolled in the study;
- A decision on the part of Sponsor to suspend, discontinue, or shorten the study;
- Study conduct at a study site may warrant termination under conditions that include the following:
 - Failure of investigator(s) to enrol eligible subjects into the study;
 - o Failure of the investigator to comply with country-specific regulations;
 - Submission of false information from the research facility to the sponsor, the clinical monitor, or a regulatory authority;
 - o Insufficient adherence to protocol requirements;
 - A conflict of interest of the investigator, his/her institution, or site personnel that could negatively impact the integrity of the clinical study;
 - o Institution or Ethics Committee under investigation for cause by a regulatory authority.

Any decision by the sponsor on stopping or restarting the study must be discussed with the investigator. All actions are to be documented and the Ethics Committee (EC) and regulatory (competent) authority notified in writing as required by local regulations. Should a protocol amendment be required, this will be managed in accordance with Section 14.1.4. The study must not recommence recruitment or dosing until approval is received in writing from the EC (if/as required by the EC).

If the study is to be terminated for safety reasons, any further administration of IMP will be stopped.

If the study is terminated for safety reasons, subjects will be followed up for a minimum of two weeks following the last exposure to IMP, at which time an End of Study visit should be conducted. Refer to Section 8.7.1 for follow up assessments. Any Aes/SAEs ongoing at the time of the End of Study visit will be followed to resolution or stabilisation (whichever is the sooner).

12. Adverse events

12.1 Definitions

12.1.1 Adverse event

An adverse event is any untoward medical occurrence in a patient or clinical investigation subject administered a pharmaceutical product and may not necessarily have a causal relationship with the administered treatment.

An AE can therefore be any unfavourable and unintended sign (including an abnormal laboratory finding), symptom, or disease temporally associated with the use of a medicinal (investigational) product, whether or not it is related to the medicinal (investigational) product. This includes an exacerbation of pre-existing conditions or events, intercurrent illnesses, drug interaction or any worsening (i.e. any clinically significant adverse change in frequency and/or intensity) of a pre-existing condition, which is temporally associated with the use of the sponsor's product. Anticipated fluctuations of pre-existing conditions, including the disease under study, that do not represent a clinically significant exacerbation or worsening need not be considered Aes.

Laboratory reference ranges are defined by upper or lower limits of parameters of the respective laboratory. The investigator should ensure that each parameter out of the normal range is assessed for clinical significance and the potential for being an AE (refer to Section 12.3). An adverse event is defined as 'serious' when it meets one of the pre-defined outcomes as described in Section 12.1.6.

12.1.2 Adverse drug reaction/Suspected adverse (drug) reaction

An adverse drug reaction (ADR) is any AE for which there is a reasonable possibility that the drug caused the AE. Reasonable possibility means there is evidence to suggest a causal relationship between the IMP and the adverse event.

12.1.3 Suspected unexpected serious adverse reactions

Suspected unexpected serious adverse reactions (SUSARs) are Aes that are believed to be related to an IMP and are both unexpected (i.e. the nature or intensity is not expected from the information provided in the Investigator's Brochure) and serious. SUSARs are subject to expedited reporting to the applicable regulatory authorities.

For regulatory reporting purposes, SUSARS will be unblinded.

12.1.4 Causality

The investigator must assign causality to each adverse event in relation to the IMP based on the following definitions:

Not related: AE with an incompatible time relationship to IMP administration, and that could

be explained by underlying disease or other drugs or is incontrovertibly not

related to the Investigational Product

Possibly related: AE with a reasonable time relationship to IMP administration, but which also

could be explained by concurrent disease or other medications.

Probably related: AE with a reasonable time relationship to IMP administration that is unlikely to be

attributed to concurrent disease or other medications.

Definitely related: AE with plausible time relationship to IMP administration and which cannot be

explained by concurrent disease or concomitant medications.

12.1.5 Severity (Intensity) of adverse event

Grade refers to the intensity of an AE and should not be confused with seriousness (refer Section 12.1.6).

Grade 1 Mild; asymptomatic or mild symptoms; clinical or diagnostic observations only;

intervention not indicated.

Grade 2 Moderate; minimal, local or noninvasive intervention indicated; limiting age-

appropriate instrumental Activities of Daily Living (ADL*).

Grade 3 Severe or medically significant but not immediately life-threatening;

hospitalisation or prolongation of hospitalisation indicated; disabling; limiting

self-care ADL**.

Grade 4 Life-threatening consequences; urgent intervention indicated.

Grade 5 Death related to AE.

Activities of Daily Living (ADL)

*Instrumental ADL – refers to preparing meals, shopping for groceries or clothes, using the telephone, managing money, etc.

**Self-Care ADL – refers to bathing, dressing and undressing, feeding self, using the toilet, taking medications, and not bedridden.

12.1.6 Serious adverse event

A serious adverse event (SAE) is any untoward medical occurrence or effect that, at any dose:

- Results in death,
- Is life-threatening.

Life-threatening in the definition of serious refers to an event in which the subject was at risk of death at the time of the event, it does not refer to an event which hypothetically might have caused death if it were more severe.

Requires inpatient hospitalisation or prolongation of existing hospitalisation.

Hospitalisation is defined as inpatient admission or care regardless of duration. Out-patient treatment in an emergency room is not in itself an SAE, although the reasons for it may be. Elective surgery, or hospital admissions and/or surgical operations planned before or during this study are not considered Aes if the illness or disease existed before the subject was enrolled in the study, provided that it did not deteriorate in an unexpected way during the study.

- Results in persistent or significant disability/incapacity.
- Is a congenital anomaly/birth defect.
- Is medically important or is a medically significant event.

Medical and scientific judgement is required to decide if prompt notification is required in situations that the investigator regards as medically important that did not strictly meet the criteria above but may have jeopardised the subject or required intervention to prevent one of the outcomes listed above, or that would suggest any significant hazard, contraindication, side effect or precaution that may be associated with the use of the IMP. Such events should also be considered as serious.

12.2 Recording of adverse events

For Australian sites, all events from Screening to prior to the first dose of IMP will be captured as medical history. All events occurring during and following the first administration of IMP will be reported as Aes or SAEs (if criteria met) until the completion of the End of Study Evaluation visit.

In the UK, all SAEs will be recorded from the time of the subject signing an informed consent. All non serious Aes prior to the first dose of IMP will be captured as medical history. All events occurring during and following the first administration of IMP will be reported as Aes or SAEs (if criteria met) until the completion of the End of Study Evaluation visit.

AEs that are ongoing at the End of Study Evaluation visit will be followed up until the event has resolved or stabilised. All follow-up information will be recorded in the subject's source records. All spontaneously volunteered and enquired for, as well as observed AEs, will be recorded in the subject's source records as well as the CRF.

It is preferable that AEs and SAEs be reported as diagnoses if available, rather than individual signs and symptoms. SAEs should be reported and documented in accordance with the procedures in Section 12.4. The following data should be documented for each AE: the description of the event, start and stop dates, intensity, causality and outcome must be recorded, as well as any actions taken.

12.3 Clinical lab abnormalities and other abnormal assessments

Abnormal laboratory findings (e.g., clinical chemistry, haematology, and urinalysis) or other abnormal assessments (e.g., ECG, vital signs) per se are not reported as AEs. However, those abnormal findings that are deemed clinically significant or are associated with signs and/or symptoms must be recorded as AEs (and recorded as an SAE if they meet the criteria of being serious) as described previously. Clinically significant abnormal laboratory or other abnormal findings that are present at baseline and worsen after first dose of IMP are to be considered AEs (and SAEs if serious).

The investigator should exercise his or her medical and scientific judgment in deciding whether an abnormal laboratory finding or other abnormal assessment is clinically significant. Usually, the abnormality should be associated with a clinically evident sign or symptom, or be likely to result in an evident sign or symptom in the near term, to be considered clinically significant. A clinically significant laboratory abnormality in the absence of clinical symptoms may jeopardize the subject and may require intervention to prevent immediate consequences.

12.4 Reporting of serious adverse events

Any SAE must be reported by the investigator if it occurs during the clinical study or within 2 weeks of the subject having received the last dose of IMP, whether or not the SAE is considered to be related to the IMP. This shall include pregnancy in a female subject or in a female partner of a male study subject. Instances of death, congenital abnormality or an event that is of such clinical concern as to influence the overall assessment of safety, if brought to the attention of the investigator at any time after cessation of IMP administration and linked by the investigator to this study, should be reported to the sponsor.

The investigator must report an SAE on an SAE Report Form and forward the SAE Report Form, the AE form and the concomitant medication form to the sponsor or delegate **within 24 hours of becoming aware of the SAE** and **regardless of causality**. All pregnancies in a female subject or in a female partner of a male study subject should be reported on a Pregnancy Report Form following the same reporting process and timelines required for SAEs.

The investigator should not wait to receive additional information to document fully the event before notification of a SAE, though additional information may be requested. Where applicable, information from relevant laboratory results, hospital case records and autopsy reports should be obtained.

Follow-up information on SAEs must also be reported by the investigational site to the sponsor within the same time frame. If a non-serious AE becomes serious, this and other relevant follow-up information must also be provided within 24 hours of the investigator becoming aware.

All SAEs will be recorded in the subject's source documents and the CRF.

It is the responsibility of the sponsor to determine whether a reported SAE fits the classification of a SUSAR (refer to Section 12.1.3). If the sponsor considers the SAE to be drug related (i.e. an adverse

drug reaction), unexpected and fulfils the criteria for a Suspected Unexpected Serious Adverse Reaction (SUSAR), the sponsor has the responsibility to expedite the reporting to all concerned investigators, to the EC where required, and to the appropriate regulatory authorities within the pre-defined timelines.

The investigator must notify their EC of SAEs occurring at the site, within the time period and in accordance with requirements specified by the EC.

The sponsor and/or delegate will promptly notify all relevant investigators and the regulatory authorities of findings that could adversely affect the safety of subjects, impact on the conduct of the study or alter the ethics approval/favourable opinion of the study.

12.5 Follow-up of adverse events and serious adverse events

All AEs and all SAEs must be followed by the investigator until resolution, or until in the opinion of the investigator, the AE has stabilised or is recognised as permanent, or until the subject is lost to follow up, whichever comes first. Follow-up investigations may be necessary according to the investigator's medical judgement.

13. Statistical analysis

13.1 General considerations

The statistical analysis principles described below will be supplemented by a comprehensive statistical analysis plan (SAP) which will be finalised before the database is locked. This will contain details of methods for handling missing data, early withdrawals, and potential covariates. Any changes to the statistical analysis plan will be described and justified in the final report.

The descriptive summary for the categorical variables will include counts and percentages. The descriptive summary for the continuous variables will include number of subjects (n), means, medians, standard deviations, and minimum and maximum values. Pharmacokinetic measures will be analysed as for continuous variables. All data will be listed for all subjects. All confidence intervals (CIs) will be 95%, unless stated otherwise. All statistical analyses will be performed using SAS unless otherwise stated.

13.2 Sample size

The sample size estimation is based on the following assumptions:

- Power of 90%
- The mean change from baseline NPRS for the active treatment compared with placebo is at least
 1 unit
- Standard deviation of the change from baseline in NPRS pain score is 2
- Correlation between active and placebo response is 0.5
- The test is two sided
- The dropout rate is 20%

The number of subjects within each treatment group is also sufficient to show a statistically significant change from baseline of 2 or more points on the NPRS.

13.3 Analysis populations

13.3.1 Full Analysis Set

The Full Analysis Set (FAS) consists of all subjects enrolled and randomised into the study. The FAS population will be used for summaries of subject disposition, demographic and baseline characteristics. Subjects will be analysed according to the treatment group they were assigned at randomisation.

13.3.2 Per protocol population

A per-protocol (PP) population will be based on duration of IMP treatment and protocol deviations. This population may exclude subjects with inadequate exposure to IMP or who have other protocol deviations. Rules for this population will be included in the SAP. The PP population is the primary population to analyse efficacy endpoints. Demographic and baseline characteristics of the PP population will also be presented.

13.3.3 Safety population

The safety population consists of all randomised subjects who received at least one dose of IMP and had at least one post dose safety assessment. The safety population will be used for the analysis of safety and tolerability. Subjects will be analysed as treated, regardless of the randomised treatment assigned, if this differs from that to which the subject was randomised.

13.3.4 PK population

The PK population will include all subjects who received at least one dose of IMP, had at least one post-

dose sample collection for PK analysis and who did not have any clinically significant events or protocol deviations that may have compromised the integrity of the PK results.

13.4 Subject disposition

The total number of subjects will be summarised. The duration on study, and number of subjects terminating the study treatment early, along with the reason for early study treatment termination will also be summarised.

13.5 Analysis of efficacy data

The primary population for analysis of efficacy data is the PP population. All summary tables and results of statistical analyses will be presented for the PP population for all efficacy endpoints. In addition, all summary tables and results will be presented for the FAS population.

13.5.1 NPRS

The primary efficacy endpoint is the absolute change from baseline mean NPRS score to the end of treatment NPRS score after LAT8881, compared with the change from baseline after placebo treatment.

Daily NPRS scores for all enrolled subjects will be listed only. Mean and standard deviation of scores during the baseline period and weeks 1, 2, 3 and 4, and the absolute and percentage change from baseline in each period, will be listed for each subject and summarised for LAT8881 and placebo treatments overall and within treatment sequence for all randomised subjects and for the PP population. The maximum change in mean NPRS from baseline to weeks 1, 2, 3 and 4, determined for each subject after LAT8881and placebo, will be listed and summarised.

Mixed effects regression models will be used to compare the absolute and percentage changes from baseline to the end of each treatment for the mean NPRS scores. The models will have fixed effects for period and treatment. Baseline mean pain score within each period by treatment combination will be included as a covariate. A random effect for subject will be included to capture the repeated measures nature of the design.

The models for the primary endpoint will be expanded to compare the absolute and percentage changes from baseline for the mean NPRS scores after 1, 2 and 3 weeks of dosing with IMP in each treatment period. The model will also include a fixed effect for week (1, 2, 3 and 4), the interaction between treatment and week to assess whether the change from baseline for each treatment is different.

The mean score at each visit, change from baseline, difference between treatments in the change from baseline and corresponding 95% confidence intervals will be presented. Comparisons will be declared statistically significant if p<0.05.

In PK subjects, NPRS scores at specified times up to 6 hours on Days 1, 28, 50 and 77 will be listed and summarised. Change from pre-dose values will also be listed and summarised. Changes over time will be analysed using the same modelling approach as for the primary endpoint.

The proportion of subjects achieving at least 30% and 50% reduction in pain after four weeks treatment, as assessed by the mean NPRS score, will be summarised with the 95% confidence interval for the percentage reduction, estimated by Clopper Pearson Exact methodology. A mixed effects logistic regression model, including the same fixed and random effect terms as for the primary endpoint, will be used to assess the odds of achieving a reduction in pain at Day 28 and Day 77 with LAT8881 compared to placebo.

13.5.2 Patient reported outcomes

Baseline and end of treatment values for the BPI interference scale, SF-MPQ-2, NPSI and BDI will be listed for LAT8881 and placebo. Values at each timepoint and the change from baseline will be summarised. PGIC will be tabulated at the end of each treatment period and summarised. Differences

between the LAT8881 and placebo treatments in the change from baseline reported outcome will be analysed using the same model as for the primary endpoint.

13.5.3 Analgesic use

Paracetamol (rescue medication) use at baseline and weekly over the treatment period will be listed for each subject. The average weekly and cumulative dose of rescue paracetamol medication in each treatment period will be summarised by visit and treatment.

13.6 Analysis of safety data

13.6.1 Extent of exposure

The number of subjects exposed to study treatment, duration of exposure and total IMP administered, will be summarised.

13.6.2 Adverse events

Adverse events will be coded using the Medical Dictionary for Regulatory Activities (MedDRA) (Version 20.0 or later) and summarised by system organ class (SOC) and preferred term (PT).

A summary of the number and percentage of subjects with the following adverse events will be prepared:

- All adverse events
- Serious adverse events
- Adverse events leading to premature discontinuation of IMP
- Adverse events by intensity
- Adverse events by relationship to IMP

All summaries of adverse events will include only treatment emergent adverse events (TEAEs). Refer Section 12.1 for adverse event definitions.

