Paracetamol (rescue medication) use at baseline and weekly over the treatment period will be listed for each subject. The average weekly and cumulative dose of rescue paracetamol medication in each treatment period will be summarised by visit and treatment

All randomised subjects who receive at least one dose of IMP and have at least one post dose safety assessment will be included in the safety analysis. Adverse events will be listed individually and will be summarised by body system and preferred term. Summaries will include the number and percentage of subjects with any adverse event, with serious adverse events, adverse events leading to premature discontinuation of IMP, adverse events by intensity and adverse events by relationship to IMP. Safety laboratory data will be summarised by visit and treatment, subjects with clinically significant abnormal results will be listed.

Plasma drug concentrations and any derived pharmacokinetic parameters will be listed and summarised descriptively for all subjects who received at least one dose of IMP, had at least one post-dose sample collection for PK analysis and who did not have any clinically significant events or protocol deviations that may have compromised the integrity of the PK results.

Anticipated Study Duration:

Recruitment approximately 9 months, study duration approximately 13 months

Subject Duration:

Maximum participation duration is 17 weeks: screening and first baseline (up to 4 weeks), first treatment (4 weeks), washout (2 weeks) second baseline (1 week), second treatment (4 weeks), follow up (2 weeks).

2. Study schedule of assessments and procedures

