7.11 Dose reduction/dose adjustments

No within-subject dose reductions or adjustments are permitted. If a subject experiences an adverse event requiring (in the investigator's opinion) temporary or permanent suspension of the IMP, the subject should be withdrawn from the study (refer to Section 5.7). The maximum allowed temporary suspension of IMP before withdrawal is 3 doses in the last 10 days or 8 doses in the 28 day treatment period.

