10.5 Completion Flags

- Subjects are considered to have completed period 1 when Day 28 visit is completed.
- Subjects are considered to have completed period 2 when Day 77 visit is completed.
- Subjects are considered to have completed study when EOS at Day 91 visit is completed.

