11.1 Subject Disposition

Following categories will be summarized in subject disposition table:

- Subjects enrolled (who met all the inclusion criteria and none of the exclusion criteria) – frequency (n)
- Subjects in FAS population – frequency (n)
- Subjects in Safety Population – frequency (n) and percentage (%) based on FAS
- Subjects in Per-Protocol Population – frequency (n) and percentage (%) based on FAS

- Subjects in [REDACTED] – frequency (n) and percentage (%) based on FAS
- Subjects completed the study, subjects who attended each visit within each study period frequency (n) and percentage (%) based on FAS
- Subjects who terminated the study along with reasons - frequency (n) and percentage (%) based on FAS
- Study duration in days – n, mean and standard deviation, median, minimum, maximum

Note that FAS population will be displayed by planned treatment sequence and all other categories will be displayed by actual treatment sequence. Reasons for discontinuation will be sorted by descending order of frequency within the “Total” column.

In DDP: Table 14.1.1.1

Subject disposition, analysis populations, status of inclusion/exclusion criteria, subjects excluded from analysis population along with reasons and unblinding details will be listed by subject. In DDP: Listing 16.2.1.1, Listing 16.2.1.2, Listing 16.2.1.3 and Listing 16.2.3.1

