11.7.1.1 Overall Adverse Events

The number and percentage of subjects and number of events will be summarized by treatment overall and within each study period for the following categories:

1. All adverse events reported
2. Treatment emergent adverse events (TEAEs)
3. Serious adverse events
4. Serious treatment-emergent adverse events
5. Related treatment-emergent adverse events
6. Related treatment-emergent serious adverse events
7. Suspected unexpected serious adverse events (SUSARs)

8. Treatment-emergent adverse events led to death
9. Treatment-emergent adverse events led to study discontinuation

In DDP: Table 14.3.1.1.1, Table 14.3.1.1.2

The summary by treatment overall will only include 'New' events within each treatment. All adverse events will be listed by subject, system organ class and preferred term sorted by event start dates.

In DDP: Listing 16.2.7.1 to 16.2.7.5

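### The SAP counts AEs that end study participation where the protocol asks for AEs that stop IMP, and does not declare the change; the two counts largely coincide but can differ

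*Protocol*

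**What the plan says.** **AE summaries.** Protocol 13.6.2 lists "Adverse events leading to premature discontinuation of IMP" among the summaries to be given as number and percentage of subjects, and the synopsis has the same item. The overall AE table in SAP 11.7.1.1 has nine categories. The only one about discontinuation is item 9, "Treatment-emergent adverse events led to study discontinuation". The tables by SOC and PT (SAP 11.7.1.2) and by severity (SAP 11.7.1.3) add none.

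**Disposition.** Protocol 13.4 asks for the "number of subjects terminating the study treatment early, along with the reason for early study treatment termination". SAP 11.1 gives "Subjects who terminated the study along with reasons". SAP 10.5 adds that "Subjects are considered to have completed study when EOS at Day 91 visit is completed".

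**Link between stopping IMP and leaving the study.** Protocol 7.11 says that if, in the investigator's opinion, an AE requires "temporary or permanent suspension of the IMP, the subject should be withdrawn from the study". Protocol 11.1 also directs withdrawal when the within-subject stopping criterion is met.

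**Attribution.** SAP 10.9 assigns an AE by its start date. An AE that starts in Period 1 or washout goes to the Period 1 treatment; if it continues, it is flagged new in Period 1 and ongoing in Period 2. SAP 11.7.1.1 restricts the overall by-treatment summary to new events.

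**Declared changes.** SAP section 12 lists several departures from the protocol, including the added McNemar's test. It does not list this one.

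**The concern.** Safety and tolerability is a secondary objective (protocol 4.2), and AEs that make subjects stop the drug are a direct measure of tolerability. A study-exit count answers a slightly different question. It depends on how withdrawal is recorded, and it can include exits that occur when no capsules are due. In a crossover the count must also name the treatment being taken when the drug was stopped. A rule based on AE start date and new events only does not always do that. With about 55 subjects, such counts may be small enough for one subject to be visible in the comparison.

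**Working it through.** The plan states no figure on this point, so the check is mainly a comparison of texts, with day counts from the schedule.

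**1. Required against planned outputs**

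| Output | Protocol | SAP |
|---|---|---|
| AE summary | AEs that stop IMP early (13.6.2, synopsis) | TEAEs that end study participation (11.7.1.1, item 9) |
| Disposition | Early end of study treatment, with reasons (13.4) | End of study, with reasons (11.1) |
| Exposure | Subjects exposed, duration, total IMP (13.6.1) | Duration, mg, % compliance (11.7.3.1) |
| Declared as a change | – | Not in section 12 |

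The exposure table shows how much was taken, but not who stopped or why.

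**2. Days on and off drug (protocol 5.1)**

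- On drug: Days 1–28 and 50–77, 28 + 28 = 56 days.
- Between periods: Days 29–49, 21 days.
- Follow-up: Days 78–91, 14 days.
- Total: 56 + 21 + 14 = 91 days.

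**3. Where the two counts can part**

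*Late Period 2 stop.* Protocol 8.8 schedules the early-withdrawal visit about two weeks after the last dose. A last dose on Day 75 or 76 puts it near Day 89 or 90 (75 + 14; 76 + 14), inside the Day 91 ± 2 window of 89 to 93. SAP 10.3 maps the Day 91 and early-termination visits to one analysis visit, and SAP 10.5 defines completion by the Day 91 visit. A subject whose IMP stopped for an AE could therefore attend the remaining visits and look like a completer. The SAP has no rule for this case.

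*Exit in follow-up.* A subject who takes the last Day 77 dose and leaves before Day 91 because of an AE has completed both IMP courses. This is study discontinuation, but not premature discontinuation of IMP.

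*Exit on Days 29–49.* The Period 1 course is complete and the Period 2 course never starts. Neither document says whether this is premature discontinuation of IMP, so it cannot be classed either way without a convention.

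**4. Attribution in the overall by-treatment table**

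Take a hypothetical subject with treatment A in Period 1 and B in Period 2. An AE starts on Day 20, continues, and leads to IMP being stopped on Day 55.

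- SAP 10.9: new in Period 1 (A), ongoing in Period 2 (B).
- SAP 11.7.1.1, new events only: one count under A, none under B.
- Drug being taken at the stop: B.

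Adding a row under the present rule would not cure this; the row needs its own attribution rule.

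**5. Size per subject**

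- One subject: 1/55 = 1.8 percentage points (1/60 = 1.7 if enrolment reaches 60).
- One subject moved from one treatment to the other: 1/55 + 1/55 = 3.6 points in the difference, assuming a denominator of 55 for both treatments.

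**The case against.** The strongest reply is that the two counts coincide by design. Protocol 7.11 and 11.1 direct withdrawal when an AE stops IMP, and capsules are counted at each treatment visit (protocol 7.12). Section 7.11 also states "The maximum allowed temporary suspension of IMP before withdrawal is 3 doses in the last 10 days", or 8 doses over the 28-day period, so a sustained stop on the subject's own initiative should be found and lead to withdrawal. Most of this stands. What remains is a stop within the last few doses, or a stop that a site does not record as a withdrawal. Section 7.11 directs withdrawal for a temporary suspension and also allows a limited one before withdrawal; those two sentences must be reconciled.

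Two further replies stand in part. Item 9 captures stops handled as the protocol directs. The AE listings, whose layout is in a Data Display Plan not available here, may show the action taken. A listing, however, is not the number and percentage that the protocol requires.

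A reader might infer more than the documents support:

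- *That the SAP count is known to miss treatment stops.* Nothing in the SAP says item 9 is derived from the completion flags in 10.5, so the late-stop case is a gap in the rules and not a demonstrated loss.
- *That every exit in washout is misclassified.* That depends on a definition neither document gives, and allocating washout-onset AEs to the preceding treatment is an explicit rule in SAP 10.9.
- *That the planned 20% dropout (0.20 × 55 = 11 subjects), or the share of days off drug, gives the number affected.* The 20% covers non-completion for any reason, and nothing supports AE-led exits being spread evenly over days on and off drug.

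**Conclusion.** The point holds in a limited form. A tolerability summary and a disposition summary required by the protocol are missing from the SAP, related but different ones stand in their place, and the change is not declared. If sites follow 7.11 and 11.1, the discrepancy should be small. It is confined to late stops not recorded as withdrawals, exits in follow-up, and exits between periods for which no convention exists. The attribution problem is separate: it arises even with full adherence, for any AE that starts in Period 1 and leads to stopping Period 2 IMP.

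Neither the number of subjects affected nor the direction of any bias between LAT8881 and placebo can be derived from the documents. The 1.8 points per subject assumes 55 subjects in the denominator. This is a consistency correction to a secondary safety output and does not affect the primary analysis.

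**What to change.** 1. In SAP 11.7.1.1, add a row for TEAEs that caused IMP to be stopped early, based on the actions taken that protocol 12.2 requires for each AE. Assign each to the IMP being taken when it was stopped, whatever the AE start date and whether it is flagged new or ongoing.
2. State a convention for subjects who leave between periods because of an AE: whether they count in this row and, if so, under which treatment.
3. Keep the study-discontinuation row as a separate item.
4. In SAP 11.1, add early termination of study treatment with reasons, as protocol 13.4 requires.

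The cost is one or two table rows and a few sentences of SAP text. Protocol 12.2 does not specify a coded field for action on IMP, so a check may be needed that the recorded action identifies withdrawal of IMP. No new assessment is needed.
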